## 3.3.1.4.4 Imputation of Concomitant Medication Start Date

Missing CM start dates are not imputed.

## 3.3.1.4.5 Imputation of Treatment End Date

If date of end of treatment is unknown, it will be imputed as the date of last contact with the patient.

## 3.3.2 Visit Window

For the purpose of the statistical analysis, study findings are allocated to the analysis visit using analysis visit windows as described in Table 2, Table 3, Table 4, Table 5, Table 6, Table 7, and Table 8. Note, study day 1 refers to the date the participant received the first dose of IP.

Table 2 Analysis Visit Windows, Biopsy

Analysis Visit	Target Day	Day Range
Week 48	337	1 through end of study

Table 3 Analysis Visit Definitions, 12-lead dECG, Vital Signs, Abbreviated Physical Examination

Analysis Visit	Target Day	Day Range
Week 4	29	2-42
Week 8	57	43-70
Week 12	85	71-98
Week 16	113	99-126
Week 20	141	127-154
Week 24	169	155-196
Week 32	225	197-252
Week 40	281	253-308
Week 48	337	309-351
Week 52	365	352-385

dECG, digital electrocardiogram.

Table 4 Analysis Visit Definitions, Clinical Laboratory Assessments Including eGFR and MELD but Excluding Fasting Glucose (Safety)

Analysis Visit	Target Day	Day Range
Week 4	29	2-42
Week 8	57	43-70
Week 12	85	71-98
Week 16	113	99-126
Week 20	141	127-154
Week 24	169	155-196
Week 32	225	197-280

Table 4 Analysis Visit Definitions, Clinical Laboratory Assessments Including eGFR and MELD but Excluding Fasting Glucose (Safety)

Analysis Visit	Target Day	Day Range
Week 48	337	281-351
Week 52	365	352-385

Due to fasting at the Week 48 visit, random glucose will not be presented for the Week 48 analysis visit. eGFR, estimated glomerular filtration rate; MELD, model for end-stage liver disease.

Table 5 Analysis Visit Definitions, Amylase, Lipase, Coagulation

Analysis Visit	Target Day	Day Range
Week 24	169	2-196
Week 32	225	197-280
Week 48	337	281-378

Table 6 Analysis Visit Definitions, Calcitonin, FibroScan, FAST, Agile 3+, BARD, Fasting Serum Lipid Panel, ELF, Pro-C3, FIB-4, Fasting Plasma Glucose (Efficacy), Fasting Glucose (Safety), C-peptide, Adiponectin

Analysis Visit	Target Day	Day Range
Week 48	337	2-378

BARD, BMI, AST/ALT ratio, diabetes; ELF, enhanced liver fibrosis; FAST, FibroScan-ALT; FIB-4, fibrosis-4; Pro-C3, released N-terminal propeptide of type III collagen.

Table 7 Analysis Visit Definitions, PK, and ADA

Analysis Visit	Target Day	Day Range
Week 4	29	2-57
Week 12	85	58-127
Week 24	169	128-253
Week 48	337	254-378

ADA, anti-drug antibody; PK, pharmacokinetic(s).

Table 8 Analysis Visit Definitions, HbA1c, Urine Albumin, Creatinine

Analysis Visit	Target Day	Day Range
Week 12	85	2-127
Week 24	169	128-253
Week 48	337	254-378

HbA1c, hemoglobin A1c.

Multiple biopsy samples within an analysis visit window are not expected. Although unlikely, if multiple histology samples are collected in the Week 48 analysis visit window, then the

histology sample collected closest to the target date will be selected (using the later sample as a tiebreaker).

If multiple, valid, non-missing, continuous measurements exist in an analysis visit window, records will be chosen based on the following rules:

- 1 The record closest to the target day for that visit will be selected.
- 2 If there are 2 records that are equidistant from the target day based on date, the later record will be selected.
- 3 In general, if there is more than 1 record on the selected day, the average will be taken.
- 4 For serum creatinine, if both enzymatic and regular creatinine are measured in the course of the study, both types of tests will be analyzed as a single parameter. If both enzymatic and regular creatinine are collected from the same blood sample and are analyzable, regular creatinine will be selected for analysis.

If multiple, valid, non-missing, categorical measurements exist in an analysis visit window, records will be chosen based on the following rules:

- 1 The record closest to the target day for that visit will be selected.
- 2 If there are 2 records that are equidistant from the target day based on date, the later record will be selected.
- In general, if there is more than 1 record on the selected day, the value with the worst severity within the window will be selected (eg, abnormal will be selected over normal for safety ECG findings and '++' will be selected over '+' for urinalysis findings).

If a laboratory test was performed within the analysis visit window, the result collected under a fasting condition will be used.

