- ECGs will be recorded in triplicate after a 10-minute supine rest period, with no more than about 2 minutes between individual ECGs, completing all 3 ECGs within a maximum of about 5 minutes. ECGs should be collected prior to vital signs, PK sample collection, or other assessments as these may alter autonomic tone.
- Whenever vital signs and blood draws are scheduled for the same nominal time, the blood draws should occur last.
- At Visit 2, vital signs should be assessed prior to first dose of study intervention.
- g AE/SAEs will be collected from the time of signature of informed consent, throughout the treatment period and follow-up period.
- Assessment of injection site reactions to be conducted after injection of study intervention.

-  The post-baseline biopsy to occur within a window from -2 weeks prior to Visit 11 (Week 48) until 4 weeks after Visit 11.
- Biopsy should only be conducted as part of the E/D visit activities in participants who have received study intervention for at least 36 weeks and who are unwilling or unable to wait until Week 48. For participants who continue the study after an E/D visit and have a biopsy at the E/D visit, an additional biopsy should not be collected at Week 48. Biopsy should be scheduled within -2 weeks prior to +4 weeks after the E/D visit.
- If a site has access to appropriate FibroScan equipment, as well as compatible software and probes, they must complete the assessments per the schedule with extended visit windows. For V2, FibroScan must be performed pre-dose within extended visit window of -14 days but only for participants who meet all inclusion/exclusion criteria (including histology central read) and are determined to be eligible for randomization. For all other visits, Fibroscan must be performed within extended visit window of ±14 days. If a site does not have access to appropriate FibroScan equipment, as well as compatible software and probes, and the assessment cannot be conducted, this will not constitute a deviation from the protocol. FibroScan should be conducted in a fasting state.
- FAST score will be calculated only at sites that have the required software.
- Study intervention should be administered after all assessments have been conducted and samples have been collected.
- ADA samples will be collected prior to administration of IP.

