# **3.3.1** General Study Level Definitions

#### 3.3.1.1 Definition of Baseline

Baseline biopsy specimen refers to either historical biopsies or on-study biopsies obtained during the screening period. Central pathology review of the eligibility read will occur upon baseline biopsy specimen receipt and processing at the histopathology vendor. Central pathology review results will support patient eligibility and enrollment. This is referred to as the eligibility read and will serve as the baseline for histology analyses.

For continuous endpoints, the baseline value for statistical analysis is the last non-missing value on or prior to date and time (if available) of administration of the first dose of IP. If multiple measurements occur on the same day, the last non-missing value on or prior to the time of first dosing of study drug will be considered as the baseline value. If these multiple measurements occur at the same time or the time is not available, the average of these measurements (for continuous data) will be considered as the baseline value. For electrocardiogram (ECG) parameters, the mean of the last set of triplicate measures prior to treatment is baseline.

For categorical endpoints, the last available record on or prior to the date of the first dose of study drug will be selected. If there are ties in terms of proximity to first dose, the value with the lowest severity will be selected (eg, normal will be selected over abnormal for safety ECG findings and '+' will be selected over '++' for urinalysis findings).

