### 4.5.5.2 Presentations

ECG tables and listings will be based on the on-treatment data only in the safety population and presented for each treatment group. ECG parameters (except for the overall evaluation) will be summarized with n, mean, median, SD, minimum, and maximum, at each visit and for change from baseline.

Number and percentage of participants within each QTcF interval classes at any time during the on-treatment period will be also reported together with number and percentage of participants within QTcF increase classes at any time during the on-treatment period.

ECG parameters fulfilling potentially clinically significant criteria at any time during treatment will be summarized by treatment.

Overall evaluation will be analyzed as shift from baseline to last value in the on-treatment period.

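### Opposite tie rules for categorical ECG records at baseline and after baseline can tilt the overall-evaluation shift table towards apparent worsening if the evaluation is held per tracing

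*SAP*

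**What the plan says.** **Baseline (SAP 3.3.1.1).** "For categorical endpoints, the last available record on or prior to the date of the first dose of study drug will be selected". Ties are then broken downwards: "If there are ties in terms of proximity to first dose, the value with the lowest severity will be selected", with the example that "normal will be selected over abnormal for safety ECG findings".

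**After baseline (SAP 3.3.2, categorical records).** Rule 1: "The record closest to the target day for that visit will be selected". Rule 2 takes the later of two equidistant records. Rule 3, for more than one record on the selected day, breaks the tie upwards: "the value with the worst severity within the window will be selected (eg, abnormal will be selected over normal for safety ECG findings".

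**Replicates (Protocol 1.3.2.1, Table 4 and footnotes).** "ECGs will be recorded in triplicate after a 10-minute supine rest period, with no more than about 2 minutes between individual ECGs". ECGs are marked at V2 to V11, at the early discontinuation visit and at follow-up.

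**Use (SAP 4.5.5).** Section 4.5.5.1 lists a three-level overall evaluation beside the numeric intervals and says that replicate measurements are averaged. Section 4.5.5.2: "Overall evaluation will be analyzed as shift from baseline to last value", the last value being taken from the on-treatment period.

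**The concern.** A shift table is informative only if its two ends measure the same thing. Averaging deals with replicate intervals, but a three-level category cannot be averaged, so replicate evaluations fall to the tie rules. Those rules point in opposite directions, and both give safety ECG findings as their example. A participant whose tracings vary in the same way before and during treatment can then be recorded as normal at baseline and abnormal on treatment.

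Safety is the primary objective and is reported descriptively, so readers will take the within-arm counts at face value. The consequence would be an inflated count of on-treatment ECG worsening in each arm, with improvement almost absent from the table.

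Rule 3 also has a wording conflict. It is triggered by several records on the selected day, yet it takes the worst record within the window. The Week 24 ECG window runs over days 155-196 (SAP Table 3). Read literally, a tracing from another day could displace the one chosen by rules 1 and 2.

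**Working it through.** The plan states no figure for this point, so there is none to reproduce. The check asks how often each rule produces a shift when nothing has changed.

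**Inputs from the documents.** Three tracings per visit. About 55 participants randomized 2:1:2:1, so 55 × 2/6 = 18.3 per cotadutide dose and the same for pooled placebo.

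**Assumptions, because the documents give no values.** The evaluation is reduced to normal or abnormal. Each tracing is read abnormal with probability p, the same before and during treatment; write q = 1 - p. Within-participant correlation (ICC) is modelled by letting p follow a beta distribution with mean p and parameters p(1-ICC)/ICC and q(1-ICC)/ICC.

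**Formulas for given p** (N = normal, A = abnormal)

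- Least severe at baseline, worst after: N to A = (1-p³)(1-q³); A to N = p³q³.
- Least severe at baseline, last timed tracing after: N to A = (1-p³)p; A to N = p³q.
- Last timed tracing at baseline, worst after: N to A = q(1-q³); A to N = pq³.
- Last tracing at both ends, or one evaluation per triplicate set (read with the same p): pq each way.
- Worst at both ends: q³(1-q³) each way.
- Majority at both ends, with m = 3p²q + p³: m(1-m) each way.

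**Independent tracings, p = 0.10** (p³ = 0.001, q³ = 0.729)

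- Least severe, then worst: 0.999 × 0.271 = 27.1%; reverse 0.001 × 0.729 = 0.07%.
- Least severe, then last: 0.999 × 0.1 = 10.0%; reverse 0.001 × 0.9 = 0.09%.
- Last, then worst: 0.9 × 0.271 = 24.4%; reverse 0.1 × 0.729 = 7.3%.
- Last at both ends, or one evaluation per set: 0.1 × 0.9 = 9.0% each way.
- Worst at both ends: 0.729 × 0.271 = 19.8% each way.
- Majority at both ends: m = 0.027 + 0.001 = 0.028; 0.028 × 0.972 = 2.7% each way.

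**With correlation.** At p = 0.10 and ICC 0.8 the beta parameters are 0.025 and 0.225. Averaging the same formulas over that distribution gives:

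| Baseline / after baseline | N to A, ICC 0 | A to N, ICC 0 | N to A, ICC 0.8 | A to N, ICC 0.8 |
|---|---|---|---|---|
| Least severe / worst | 27.1% | 0.07% | 5.5% | 0.06% |
| Least severe / last | 10.0% | 0.09% | 3.1% | 0.5% |
| Last / worst | 24.4% | 7.3% | 3.5% | 0.7% |
| Last / last, or one per set | 9.0% | 9.0% | 1.8% | 1.8% |
| Worst / worst | 19.8% | 19.8% | 1.6% | 1.6% |
| Majority / majority | 2.7% | 2.7% | 1.2% | 1.2% |

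In an arm of about 18, the first row is 18.3 × 0.271 = 5 false worsenings with independent tracings and 18.3 × 0.055 = 1 at ICC 0.8, with none expected in reverse. Over p from 0.02 to 0.30 and ICC from 0 to 0.95, that row runs from 0.3% to 63.9%, with the reverse shift never above 0.9%.

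**Which row applies.** Three things are unsettled: whether the evaluation is recorded per tracing or per set, whether baseline ties are judged by date or clock time, and whether the last on-treatment value passes through the 3.3.2 rules. On the second, the categorical baseline rule refers only to the date of first dose, whereas the continuous rule uses date and time; same-day replicates therefore tie most naturally. On the third, SAP 3.3.3 sends several assessments in one window to 3.3.2, but 4.5.5.2 does not cite it.

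**The case against.** The strongest reply is that the mechanism needs a premise the documents never state. SAP 4.5.5.1 lists a single overall evaluation, with reason and clinical significance if abnormal. Protocol 8.2.4 describes an assessment of whether the findings are normal or abnormal, with the central reading prevailing. One evaluation per triplicate set would leave no triplicate tie to break. Even with per-tracing records, concordant triplicates produce no false shift, and three tracings within about 5 minutes should be well correlated. All of this stands, and it makes the point conditional. It does not remove the conflict: the SAP's own examples expect several same-day ECG findings, and the investigator may add ECGs after an abnormal one, so a same-day repeat would meet the same opposed rules.

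The mirrored examples may also reflect a deliberate preference for catching on-treatment abnormalities. Taking the worst tracing at both ends keeps the post-baseline part of that preference without the directional tilt.

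A reader might infer three stronger things that the documents do not support:

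- That the table will in fact fill with false worsening. No abnormal rate or replicate disagreement rate is given, so this cannot be established.
- That a real drug effect is hidden, or a false one created. The rule is the same in every arm, so it creates no cotadutide-placebo difference by itself, and no loss of detection has been shown.
- That the listed primary ECG assessments are compromised. Protocol Tables 1 and 8 and SAP 4.2.1 list interval values, changes, potentially clinically significant criteria and QTcF thresholds. The overall evaluation appears only in SAP 4.5.5. The interval, QTcF and potentially-clinically-significant summaries use averaged triplicates and are unaffected.

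Finally, bringing in a tracing from another day is only one reading of rule 3.

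**Conclusion.** The point holds conditionally and is minor. The two tie rules are explicit, opposed and aimed at the same kind of ECG record, and a shift from baseline is the display they feed. If the evaluation is held per tracing, replicates disagree and both tie rules act, the table can show worsening without change and almost no improvement, in all arms.

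The amount cannot be known from the documents. The percentages rest on an assumed 10% abnormal rate, a two-level evaluation and an assumed correlation; the 5.5% figure is more plausible than 27% for tracings minutes apart, but neither is an estimate for this trial. Under two readings (one evaluation per set, or the last tracing at both ends) there is no tilt. The conclusion that survives every reading is that the SAP should settle how replicate evaluations are handled and treat both ends alike.

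**What to change.** 1. In SAP 3.3.1.1 and 3.3.2, apply one rule to replicate categorical ECG records at baseline and after baseline: worst of the triplicate at both, or majority at both. Keep single abnormal tracings in the listings.
2. In SAP 4.5.5.2, say that the last on-treatment value is chosen by that rule. State in 4.5.5.1 whether the overall evaluation is recorded per tracing or per triplicate set.
3. In categorical rule 3 of 3.3.2, replace 'within the window' by 'on the selected day', so that it cannot override rules 1 and 2.

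The cost is a few SAP sentences and a small programming change; no new data are needed. Each rule has a downside. With majority, an abnormality on one of three tracings appears only in the listing. With worst at both ends, a single abnormal baseline tracing can mask a later abnormality in the shift table.

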# 3.3.3 Handling of Unscheduled Visits

If there is more than 1 assessment in the same time window, 1 assessment will be chosen for inclusion in analysis based on rules described in Section 3.3.2. All scheduled and unscheduled assessments will be presented in the listings.

# 3.3.4 Multiplicity/Multiple Comparisons

No formal hypothesis testing will be performed, and all p-values are nominal. Therefore, no adjustments for multiplicity will be made.

# 3.3.5 Handling of Protocol Deviations in Study Analysis

The list of important protocol deviations (IPDs) is provided in the Protocol Deviation Plan.

### 4 STATISTICAL ANALYSIS

The safety population will be used as the primary population for safety analyses. Efficacy analyses will be performed using the FAS and/or PP analysis sets, as appropriate.

# 4.1 Study Population

## 4.1.1 Participant Disposition and Completion Status

#### 4.1.1.1 Definitions and Derivations

None

#### 4.1.1.2 Presentation

Participant disposition of the enrolled population will be summarized overall and by treatment group (number/percent of participants meeting each milestone):

- # enrolled
- # randomized
- # receiving at least 1 dose
- # completed treatment/discontinued treatment
- # completed study/withdrew from study
- # not discontinued/discontinued from treatment at Week 48

Randomization code and assigned kit ID will also be listed.

A listing including all standardized disposition terms will be also provided for all discontinued participants. Both the table and the listing will be based on the all enrolled participants population.

# 4.1.2 Analysis Sets

#### 4.1.2.1 Definitions and Derivations

The analysis sets are defined in Section 3.2.

#### Possible reasons for exclusion from analysis sets will be:

- Randomized set: Participant not randomized.
- FAS: Participant not randomized OR participant did not receive at least 1 dose of the IP.
- PP: Participant not randomized OR participant did not receive at least 1 dose of the IP OR did not have evaluable post-baseline biopsy after at least 36 weeks of treatment OR participant excluded due to site GCP concerns (Site PPD
- Safety set: Participant did not receive at least 1 dose of the IP.

• PK (pharmacokinetics) set: Participant did not receive at least 1 dose of the IP OR participant did not have at least 1 detectable cotadutide concentration.

#### 4.1.2.2 Presentation

The number and percentage of participants belonging to each analysis set and excluded for each possible reason will be presented in a summary table overall and by treatment group in each part. The table will be based on the all enrolled participants population. Listings of all randomized participants excluded from the FAS, PP, safety, or PK population will be also provided including reason for exclusion from the population.

#### 4.1.3 Protocol Deviations

#### 4.1.3.1 Definitions and Derivations

The protocol deviations will be captured during the study. IPDs are described in Section 3.3.5.

#### 4.1.3.2 Presentation

The number and percentage of participants with at least 1 IPD will be summarized for each treatment group and overall in each part in the FAS population. All IPDs will be also listed for all participants included in the FAS population.

# 4.1.4 Demographics

#### 4.1.4.1 Definitions and Derivations

Demographic variables include age, age category (< 50 years;  $\ge 50$  to < 65 years;  $\ge 65$  years), sex, race, ethnic group, region, and country. Age at screening and year of birth is collected directly on the CRF; month and day of birth will not be entered. The age at screening used for analysis will be the directly entered value. For determination of age post-screening, refer to Section 4.2.3.2.

Regions will be defined as:

- US: United States
- Asia: Japan, South Korea, Malaysia, Thailand, and Taiwan
- Rest of World: (all other countries)

## 4.1.4.2 Presentation

Demographic variables will be summarized for each treatment group and overall in the FAS population. They will be also listed for all participants included in the FAS population.

### 4.1.5 Baseline Characteristics

#### 4.1.5.1 Definitions and Derivations

Baseline characteristics include height (cm), weight (kg), body mass index (BMI) (kg/m^2), and BMI category. BMI (kg/m^2) is calculated as weight (kg) divided by the square of height (cm)/100.

#### 4.1.5.2 Presentation

Baseline variables will be summarized for each treatment group and overall in the FAS population. Continuous variables will be summarized using n, mean, median, standard deviation (SD), minimum, and maximum; categorical variables will be summarized using number and percent of participants.

# 4.1.6 Disease Characteristics

#### 4.1.6.1 Definitions and Derivations

sease characteristics and comorbidities include baseline liver fibrosis stage (F2 and F3) and T2DM status, Non-alcoholic Fatty Liver Disease (NAFLD) Activity Score (NAS) (overall score and steatosis, lobular inflammation, and ballooning components), FibroScan (liver stiffness measurement [LSM] and controlled attenuation parameter [CAP]), enhanced liver fibrosis (ELF) score, CMs of vitamin E and pioglitazone, lipids (total cholesterol, high-density lipoprotein [HDL], low-density lipoprotein [LDL], triglycerides), ALT, AST, gamma glutamyl transferase (GGT), liver biomarkers (Pro-C3, FIB-4, APRI, NFS, BARD score, FibroScan-AST [FAST] score, and Agile 3+). Hemoglobin A1c (HbA1c) will be analyzed as a continuous variable as well as categorically (< 5.7%, 5.7% to 6.4%, ≥ 6.5%). Model for End-Stage Liver Disease (MELD) score, fasting plasma glucose, (total and high molecular weight) adiponectin, C-peptide, and systolic blood pressure (SBP) at baseline will be included. Use of lipid-lowering therapies or T2DM therapies will be included.

If both direct and calculated LDL lab codes are entered, they will be combined into a single parameter for analysis and used interchangeably.

Details of screening biopsy (as an on-study procedure or from a historical sample) will be summarized by treatment group, including timing relative to randomization.

